### 3.7 Subject Evaluation Methods

#### 3.7.1 Routine Laboratory Evaluations

Routine laboratory tests (hematology, serum chemistry, and urinalysis) during screening and during the study (see [Table 3.6-1](#), [Table 3.6-2](#), and [Table 3.6-3](#)) will be performed in a licensed local clinical laboratory. Urine pregnancy tests during the study will be performed in the clinic using a licensed test. Abnormal laboratory results should be repeated as soon as possible (preferably within 24 to 48 hours).

Creatinine clearance (CrCl) will be calculated using the Cockcroft-Gault formula ([Cockcroft and Gault, 1976](#)) as shown in [Table 3.7.1-1](#).

**Table 3.7.1-1 Creatinine Clearance Calculation**

For Women	$\text{CrCl} = \frac{[140 - \text{Age (years)}] \times \text{Mass (kg)} \times 0.85}{72 \times \text{serum creatinine (mg/dl)}}$ 
or
 $\text{CrCl} = \frac{[140 - \text{Age (years)}] \times \text{Mass (kg)} \times 0.85}{815 \times \text{serum creatinine (mmol/L)}}$
For Men	$\text{CrCl} = \frac{[140 - \text{Age (years)}] \times \text{Mass (kg)}}{72 \times \text{serum creatinine (mg/dl)}}$ 
or
 $\text{CrCl} = \frac{[140 - \text{Age (years)}] \times \text{Mass (kg)}}{815 \times \text{serum creatinine (mmol/L)}}$

#### 3.7.2 Physical Examination and Vital Signs

Physical examinations will be performed as described in [Table 3.6-1](#) and [Table 3.6-2](#) (screening and treatment visits), and [Table 3.6-3](#) (follow-up visits) and will include assessments of the head, eyes, ears, nose, and throat (HEENT), respiratory, cardiovascular, gastrointestinal, urogenital, musculoskeletal, neurological, psychiatric, dermatological, hematologic/lymphatic, and endocrine systems; and height (at screening only).

Vital signs (temperature, blood pressure, pulse rate, and respiratory rate) will be performed as described in [Table 3.6-1](#) and [Table 3.6-2](#). On treatment days vital signs will be performed prior to and 15, 30, and 45 minutes ( $\pm 5$  minutes) post initiation of infusion with MEDI-575,

at the completion of the infusion ( $\pm 5$  minutes), and 30 and 60 minutes ( $\pm 5$  minutes) post completion of the infusion with MEDI-575.

### **3.7.3 Electrocardiographic Evaluations**

Twelve-lead ECGs will be performed as described in [Table 3.6-1](#), [Table 3.6-2](#), and [Table 3.6-3](#). Electrocardiogram equipment, with instant print-out and electronic transmission capabilities, and training will be provided to all study sites. All ECGs performed during the study will be obtained in triplicate (ie, 3 ECGs should be obtained within a 5-minute time period). The ECGs will be collected at screening, Cycle 1, Study Day 1 and Study Day 8 (Dose Cohort 1, only) (prior to infusion, at the time of completion of infusion [ $\pm 5$  minutes], 2 hours post completion of infusion [ $\pm 15$  minutes], and 6 hours [ $\pm 15$  minutes] post completion of infusion), Study Day 1 of all subsequent cycles prior to dosing, at the time of discontinuation of MEDI-575, and at 30 days after the last dose of MEDI-575. All ECGs should be done prior to the PK draw for corresponding time points. Electrocardiograms will be transmitted and interpreted by a central vendor selected by the sponsor.

### **3.7.4 Pharmacokinetic and Immunologic Evaluations**

Blood samples for assessment of PK parameters for MEDI-575 and anti-MEDI-575 antibodies will be collected as described in [Table 3.6-1](#), [Table 3.6-2](#), and [Table 3.6-3](#)

Details for collection, aliquoting, storage, and shipment of serum samples for PK and IM evaluations are presented in the Specimen Collection Manual provided by the sponsor.

### **3.7.5 Disease Evaluations**

Tumor measurements and assessments will be based on RECIST guidelines ([Therasse et al, 2000](#)) and will be performed as specified in [Table 3.6-1](#) and [Table 3.6-2](#), and a schedule of follow-up visit procedures is presented in [Table 3.6-3](#). Additional tumor measurements may be performed at the discretion of the investigator or according to institutional practice. In subjects who achieve a complete or partial response to treatment, tumor measurements will be repeated at least 4 weeks later using the same imaging tests. The same tumor assessment method should be used throughout the treatment period.

Tumor measurements must be recorded in metric notation by use of a ruler or calipers, and the same method/technique of tumor assessment must be used throughout the study. Imaging-

based evaluation is preferred to evaluation by clinical examination when both methods have been used to assess the antitumor effect of the treatment. The analysis for tumor response will be based on the investigator's assessment during the conduct of the study. Radiographic images may be collected and archived by the sponsor or its designee.

Tumor assessments may include the following evaluations: physical examination; chest radiograph (x-ray); CT or MRI scan of the chest, abdomen, and pelvis; and CT or MRI scan of the brain. A CT scan or MRI of the brain will be performed if the subject is neurologically symptomatic. The same method must be used for all subsequent tumor assessments.

- Physical examination. Lesions detected by physical examination will only be considered measurable if superficial, eg, skin nodules and palpable lymph nodes. Documentation by color photography including ruler is recommended for estimating the size of skin lesions.
- Chest x-ray. Lesions considered acceptable for measurement on chest radiograph should be clearly defined and surrounded by aerated lung; however, CT is preferable.
- CT scans of the chest, abdomen, and pelvis. The CT should be performed with contiguous cuts in slice thickness of 10 mm or less. Spiral CT should be performed using a 5-mm contiguous reconstruction algorithm.
- MRI scans. MRI is acceptable for measurement of lesions provided that the same anatomical plane is used for serial assessments. If possible, the same imaging device should be used for serial evaluations. In case of MRI, measurements will be preferably performed in the axial (transverse) plane on contrast enhanced T1-weighted images; however, there are no specific sequence recommendations.

### **Measurability of Tumor Lesions at Screening**

At screening, tumor lesions will be categorized as follows:

- **Measurable Lesions** - Measurable lesions are defined as those that can be accurately measured in at least one dimension (longest diameter [LD] to be recorded) as  $\geq 20$  mm with conventional techniques (CT, MRI, x-ray) or as  $\geq 10$  mm with spiral CT scan. All tumor measurements must be recorded in millimeters by use of a ruler or calipers.
- **Nonmeasurable Lesions** - Nonmeasurable lesions are defined as all other lesions (or sites of disease), including small lesions ( $LD < 20$  mm with conventional techniques or  $< 10$  mm using spiral CT scan). Lesions considered truly nonmeasurable include the following: bone lesions, leptomeningeal disease, ascites, pleural/pericardial effusion, inflammatory breast disease, lymphangitis cutis/pulmonis, abdominal masses that are not confined and followed by imaging techniques, and cystic lesions.

- **Target Lesions** - All measurable lesions up to a maximum of 5 lesions per organ and 10 lesions in total, representative of all involved organs, should be identified as target lesions and recorded at screening. Target lesions should be selected on the basis of their size (those with the longest diameter) and their suitability for accurate repeated measurements (either by imaging techniques or clinically). A sum of the LD for all target lesions will be calculated and reported as the baseline sum LD. The baseline sum LD will be used as the reference by which to characterize the objective tumor response.
- **Non-Target Lesions** - All other lesions (or sites of disease) should be identified as non-target lesions and should also be recorded at screening. Measurements of these lesions are not required, but the presence or absence of each should be noted throughout the study.

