## **1 Introduction**

### **1.1 Background**

Platelet-derived growth factors (PDGFs) are peptide growth factors that stimulate cellular growth, proliferation, and differentiation ([Fredriksson et al, 2004](#)). The PDGFs exert their cellular effects through transmembrane receptor tyrosine kinases, PDGF receptor alpha (PDGFR $\alpha$ ) and PDGF receptor beta (PDGFR $\beta$ ). PDGFR $\alpha$  plays an important role in human carcinogenesis, both as a direct target on tumor cells and also as a mediator of stromal support for cancer cell growth. Genetic modifications leading to overexpression or activation of PDGFR $\alpha$  have been demonstrated in at least 3 different malignancies. In glioblastoma multiforme (GBM), an internal deletion leads to ligand-independent signaling in malignant cells ([Shih and Holland, 2006](#)); in gastrointestinal stromal tumors (GIST), small deletions and point mutants lead to independent activation ([Corless et al, 2004](#)); and in chronic eosinophilic leukemia (CEL), a fusion of FIP1L1 and PDGFR $\alpha$  leads to aberrant activation of PDGFR $\alpha$  in eosinophil and other hematopoietic precursors, leading to excessive proliferation ([Buitenhuis et al, 2007](#)).

Inhibition of PDGFR $\alpha$  signaling has been used as an effective therapeutic strategy in those diseases where such signaling is known to be important for tumor progression. For example, in patients with CEL who have the FIP1L1-PDGFR fusion (between the genes for PDGFR $\alpha$  and FIP1L1 in chromosome 4 coding for a constitutively activated PDGFR $\alpha$  tyrosine kinase), treatment with imatinib, a tyrosine kinase inhibitor with activity against PDGFR $\alpha$ , led to 100% response whereas, when the receptor was not expressed, the response rate was only 14% ([Baccarani et al, 2007](#)). PDGFR $\alpha$  inhibitors have also been shown to be useful in GIST ([Sleijfer et al, 2008](#)). The use of currently available small molecule PDGFR inhibitors is limited in part by toxicities related to inhibition of PDGFR $\beta$ , which is thought to mediate the extravascular fluid accumulation that is observed with agents such as imatinib and dasatinib ([Jayson et al, 2005](#); [Quintás-Cardama et al, 2007](#)). Targeting PDGFR $\alpha$  specifically with a

small molecule inhibitor has not yet been accomplished clinically, and may be difficult due to the high degree of structural similarity between the 2 isoforms of the receptor.

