#### 3.1.1 Inclusion Criteria

Subjects must meet *all* of the following criteria:

- 1) Men or women at least 18 years of age or older at time of study entry
- 2) Written informed consent and HIPAA authorization (applies to covered entities in the USA only) obtained from the subject/legal representative prior to performing any protocol-related procedures, including screening evaluations
- 3) Women of child-bearing potential, unless surgically sterile (including tubal ligation) or at least 1 year post menopause, must have used 2 effective methods of avoiding pregnancy (including oral, transdermal, or implanted contraceptives, intrauterine device, female condom with spermicide, diaphragm with spermicide, cervical cap, abstinence, use of a condom with spermicide by the sexual partner, or sterile sexual partner) from the time of signing the informed consent, and must agree to continue using such precautions for 30 days after the final dose of investigational product; cessation of birth control after this point should be discussed with a responsible physician

- 4) Men, unless surgically sterile, with their female partners (unless surgically sterile or 1 year post menopause) must use 2 effective methods of birth control as described in item 3 and must agree to continue using such contraceptive precautions from Cycle 1, Study Day 1 through 30 days after the final dose of investigational product
- 5) Histologically confirmed advanced solid tumor for which no curative or standard therapies exist
  - The 12 additional subjects treated in the dose-expansion phase must have measurable disease (as defined in Section 3.7.5), and a histologically-confirmed diagnosis of NSCLC, GBM, ovarian cancer, or synovial sarcoma.
- 6) Karnofsky performance status of  $\geq 60$  (see Appendix 1)
- 7) Life expectancy of  $\geq 12$  weeks
- 8) Prior radiation therapy is allowed provided exposure does not exceed an area of 25% of marrow space
- 9) Toxicities from previous cancer therapies must have recovered to  $< \text{Grade } 2$
- 10) Prothrombin time elevation  $\leq \text{Grade } 2$  is acceptable for subjects on anticoagulant therapy
- 11) Adequate hematologic function defined as:
  - Hemoglobin  $\geq 10$  g/dL
  - Absolute neutrophil count  $\geq 1500/\text{mm}^3$
  - Platelet count  $\geq 100,000/\text{mm}^3$
- 12) Adequate organ function defined as follows:

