### 3.1.2 Exclusion Criteria

Any of the following would exclude the subject from participating in the study:

- 1) Any concurrent chemotherapy, radiotherapy, immunotherapy, biologic, or hormonal therapy for treatment of cancer
- 2) Previous mAb treatment specifically directed against PDGF or PDGF receptors
- 3) History of allergy or reaction to any component of the MEDI-575 formulation
- 4) Receipt of any chemotherapy regimens within 4 weeks prior to the first dose of MEDI-575
- 5) Receipt of any biological or immunological based therapies (including, but not limited to, mAb therapy such as bevacizumab or cancer vaccine therapies) within 6 weeks prior to the first dose of MEDI-575
- 6) Receipt of any investigational anticancer therapy within 4 weeks prior to the first dose of MEDI-575
- 7) Major surgery (defined as invasive abdominal, pelvic, cardiothoracic, neurological, orthopedic or vascular surgery) within 4 weeks of receipt of MEDI-575 or minor surgery (superficial surgery with minimal invasiveness) within 2 weeks prior to receipt of MEDI-575. All surgical wounds must be without healing complications such as infection or dehiscence
- 8) New York Heart Association  $\geq$  Grade 2 congestive heart failure
- 9) History of myocardial infarction, unstable angina, transient ischemic attack or stroke within the previous 6 months prior to the first dose of MEDI-575
- 10) History of other invasive malignancy within 5 years except for cervical carcinoma in situ (CIS), non-melanomatous carcinoma of the skin or ductal carcinoma in situ (DCIS) of the breast that have been surgically cured
- 11) Evidence of significant active infection requiring antimicrobial, antifungal, antiparasitic, or antiviral therapy or for which other supportive care is given
- 12) Use of immunosuppressive medication (inhaled and topical corticosteroids are permitted) within 7 days prior to the first dose of MEDI-575
- 13) Systemic immunosuppressive steroid therapy. Subjects may take replacement doses of steroids (defined as  $\leq$  30 mg day hydrocortisone or the equivalent) if on a stable dose for at least 2 weeks prior to receipt of MEDI-575
- 14) Known brain metastases
- 15) Pregnancy or lactation
- 16) Previous medical history or evidence of an intercurrent illness that may, in the opinion of the investigator, compromise the safety of the subject in the study
- 17) Clinically significant abnormality on ECG

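### Irradiated lesions can be target lesions and prior radiotherapy has no treatment-free interval, so radiation shrinkage can be scored as a partial response to MEDI-575

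*Protocol*

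**What the plan says.** **Eligibility (Protocol 3.1.1 and 3.1.2).** Exclusion 1 bars "Any concurrent chemotherapy, radiotherapy, immunotherapy, biologic, or hormonal therapy for treatment of cancer". Three later criteria set an interval before the first dose:

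- Exclusion 4: "Receipt of any chemotherapy regimens within 4 weeks prior to the first dose of MEDI-575".
- Exclusion 5 reads: "Receipt of any biological or immunological based therapies (including, but not limited to, mAb therapy such as bevacizumab or cancer vaccine therapies) within 6 weeks".
- Exclusion 6: "Receipt of any investigational anticancer therapy within 4 weeks prior to the first dose of MEDI-575".

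On radiotherapy, Inclusion 8 says only: "Prior radiation therapy is allowed provided exposure does not exceed an area of 25% of marrow space". Exclusion 2 bars "Previous mAb treatment specifically directed against PDGF or PDGF receptors" and does not mention small molecules. Inclusion 9 requires toxicity from earlier cancer treatment to have fallen below Grade 2.

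**Baseline and lesion choice (Protocol 3.6, Screening, and 3.7.5).** Screening procedures, including the CT or MRI scan, may be done up to 28 days before the first dose. Target lesions are "All measurable lesions up to a maximum of 5 lesions per organ and 10 lesions in total". They are to represent the involved organs and are chosen by size and by how reliably they can be measured again. Whether a lesion has been irradiated plays no part.

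**Scoring (Protocol 3.7.5 and 5.5.3).** A PR is a fall of 30% or more in the sum of longest diameters (LD) from baseline. Objective response rate (ORR) counts responses that are still present on repeat imaging 4 weeks or more later. The investigator's assessment is used.

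**The concern.** The protocol sets an interval for most kinds of earlier treatment, including surgery (Exclusion 7) and immunosuppressive drugs (Exclusion 12). Radiotherapy and hormonal therapy are barred when concurrent but have no interval. A subject could finish radiotherapy shortly before Study Day 1, or even after the baseline scan, and still be eligible. The irradiated lesion would then normally enter the baseline sum, and its later shrinkage would be credited to MEDI-575.

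The trial is single-arm, so no comparison group would reveal the carry-over. Responses could matter in two places. Section 4.9, Item 6 lets efficacy data from the escalation cohorts, where available, enter the choice of both expansion doses. Section 2.4 says the every-3-week regimen will be compared with the weekly one in the expansion phase, at about 6 subjects each. In groups that small, one misattributed response is visible in the result.

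**Working it through.** **1. Coverage of earlier treatments**

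| Earlier treatment | Barred if concurrent (Exclusion 1) | Interval before first dose |
|---|---|---|
| Chemotherapy | yes | 4 weeks (Exclusion 4) |
| Biological or immunological | yes | 6 weeks (Exclusion 5) |
| Investigational anticancer agent | not named as a class | 4 weeks (Exclusion 6) |
| Radiotherapy | yes | none; marrow-area limit only (Inclusion 8) |
| Hormonal therapy | yes | none |
| Marketed small-molecule PDGFR inhibitor | not named | only if read as chemotherapy, which the protocol does not say |

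The last row is a real class in this protocol. Section 1.1 speaks of PDGFR inhibitors already available and of their use in gastrointestinal stromal tumors, which the escalation criteria do not exclude.

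**2. When an irradiated lesion alone gives a PR**

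Inputs: the 30% PR threshold (Section 3.7.5); w, the irradiated lesion's share of the baseline sum LD; s, its fractional shrinkage. The other target lesions are assumed static.

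Fall in the sum = w × s. A PR needs w × s ≥ 0.30, so s ≥ 0.30 / w.

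| w | shrinkage needed, 0.30 / w |
|---|---|
| 1.00 | 30% |
| 0.75 | 40% |
| 0.50 | 60% |
| 0.40 | 75% |
| 0.30 | 100% |
| 0.25 | 120%, impossible |

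Example: the baseline sum is 100 mm, of which an irradiated lesion is 40 mm. It shrinks to 10 mm and the rest stays at 60 mm. The new sum is 60 + 10 = 70 mm, and (100 − 70) / 100 = 30%, which is a PR. Below a 30% share, the lesion cannot produce a PR unless the others shrink too. Inclusion 14 asks expansion subjects for only one measurable lesion. For a subject with exactly one, w = 1 and 30% shrinkage is enough.

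**3. Effect of one such case on ORR** (exact Clopper-Pearson 95% intervals)

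| Group | No response | One carry-over response |
|---|---|---|
| One expansion schedule, n = 6 | 0/6 = 0% (0 to 45.9%) | 1/6 = 16.7% (0.4 to 64.1%) |
| Both schedules, n = 12 | 0/12 = 0% (0 to 26.5%) | 1/12 = 8.3% (0.2 to 38.5%) |

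In an escalation cohort of 3, one response is 1/3 = 33.3%.

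The protocol reports no figure of its own on this point, so there is none to reproduce. It also gives no basis for how often recent radiotherapy would occur.

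**The case against.** The best defence of the plan has four parts.

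- **ORR is secondary.** It has no hypothesis test and no response threshold, and dose choice rests mainly on PK, pharmacodynamics and safety. This stands and limits the weight of the point.
- **A response must be confirmed.** The 4-week confirmation removes transient changes. It does not help if radiation shrinkage persists, which is the case of concern.
- **The scenario is demanding.** The 40 mm example sits exactly on the threshold and needs 75% shrinkage. This is fair for subjects with several lesions, but not for a subject with one measurable lesion.
- **Section 3.7.5 refers to RECIST.** That source is not at hand, so no rule on irradiated lesions can be assumed from it. The protocol's own selection text contains none.

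It is also true that Exclusion 1 and Exclusions 4 to 6 do not contradict each other. Their lists cover different treatments, and the protocol does not say whether that is deliberate.

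A reader might infer more than the text supports:

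- **That small-molecule PDGFR inhibitors have no washout at all.** Exclusion 6 gives 4 weeks for investigational ones. Only marketed agents are left unassigned.
- **That carry-over toxicity will be counted as dose-limiting.** Inclusion 9 screens out unresolved toxicity, and Section 4.10 does not count an event that another cause reasonably explains. Sections 1.4 and 2.4 report no dose-limiting toxicity in Cohorts 1 to 5. What remains is delayed toxicity that appears after entry and is misattributed.
- **That the trial tests whether MEDI-575 avoids fluid accumulation.** Section 1.1 links this to PDGFR-beta, "which is thought to mediate the extravascular fluid accumulation that is observed with agents such as imatinib and dasatinib". Section 1.2 presents its avoidance as a theoretical advantage, and no objective tests it.
- **That residual kinase inhibition would distort the PDGF-AA results.** The schedule takes a plasma biomarker sample before the first infusion, and the protocol gives no figure for such an effect.

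**Conclusion.** The point holds for response. Under the eligibility and lesion-selection text as written, a recently irradiated lesion can enter the baseline sum, and its shrinkage can be scored as a confirmed PR to MEDI-575. With the other lesions static, this requires the lesion to hold at least 30% of that sum. One case moves ORR from 0/6 to 1/6 (16.7%) in an expansion schedule. The result assumes that the shrinkage lasts through confirmation and that such a subject is enrolled; the documents support no estimate of how likely that is.

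The consequence is for a secondary, descriptive endpoint in an uncontrolled trial with very small groups. The toxicity side is minor, since it concerns only delayed events misattributed despite the existing safeguards. The missing interval for hormonal therapy and the unassigned status of marketed small-molecule PDGFR inhibitors are matters for the sponsor to clarify. The change to the lesion rule is worth making because it is cheap and removes a definite scoring flaw.

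**What to change.** **Target-lesion rule.** In Section 3.7.5, under measurability at screening, state that a previously irradiated lesion may be a target lesion only if it has progressed since radiotherapy, and is otherwise recorded as non-target. Such a lesion is still followed for progression and still counts in the overall response table. A lesion irradiated after the baseline scan could not meet the condition and would be non-target.

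**Data.** Record the date and field of the last radiotherapy, so that each response can be listed against them.

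**Eligibility lists.** Reconcile Exclusion 1 with Exclusions 4 to 6. State whether leaving radiotherapy, hormonal therapy and marketed small-molecule PDGFR inhibitors out of the timed criteria is intended. No interval is proposed here; that is for the sponsor.

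**Cost.** Amendment wording and two baseline data items. An occasional expansion subject whose only measurable lesion was irradiated without later progression would no longer have measurable disease, and so would not meet Inclusions 5 and 14.
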